### 3.2. Exclusion Criteria

1. Subject should not be receiving any agent for fatigue including steroids or megace.  
**NOTE:** Subjects who have a contrast-induced allergy are allowed to receive steroids for their scans.
2. Radiotherapy within 2 weeks prior to study registration. Subjects must have recovered from all therapy-related toxicities.
3. Prior treatment with regorafenib.
4. Previous assignment to treatment during this study. Subjects permanently withdrawn from study participation will not be allowed to re-enter study.
5. Congestive heart failure > New York Heart Association (NYHA) class 2.
  - Unstable angina (angina symptoms at rest), new-onset angina (begun within the last 3 months). Myocardial infarction less than 6 months before study registration.
  - Cardiac arrhythmias requiring anti-arrhythmic therapy (beta blockers or digoxin are permitted).
  - Uncontrolled hypertension (systolic blood pressure > 150 mmHg or diastolic pressure > 90 mmHg despite optimal medical management).
6. Evidence or history of bleeding diathesis or coagulopathy.
7. Any hemorrhage or bleeding event  $\geq$  NCI CTCAE Grade 3 within 4 weeks prior to study registration.
8. Subjects with thrombotic, embolic, venous, or arterial events, such as cerebrovascular accident (including transient ischemic attacks), deep vein thrombosis or pulmonary embolism within 6 months of study registration.
9. Previous or concurrent cancer that is distinct in primary site or histology from colorectal cancer within 3 years prior to randomization EXCEPT for curatively treated cervical cancer in situ, non-melanoma skin cancer and superficial bladder tumors [Ta (Non-invasive tumor), Tis (Carcinoma in situ) and T1 (Tumor invades lamina propria)].
10. Subjects with pheochromocytoma.
11. Known history of human immunodeficiency virus (HIV) infection or current chronic or active hepatitis B or C infection requiring treatment with antiviral therapy.
12. Ongoing infection > Grade 2 NCI-CTCAE v4.0.
13. Metastatic brain or meningeal tumors (symptomatic or asymptomatic).

14. Major surgical procedure or significant traumatic injury, as defined by the site investigator, within 28 days before study registration.
15. Renal failure requiring hemo- or peritoneal dialysis.
16. Dehydration Grade > 2 NCI CTCAE v4 within 7 days prior to registration.
17. Subjects with seizure disorder currently requiring medication.
18. Persistent proteinuria  $\geq$  Grade 3 NCI CTCAE v4.0 as defined as  $> 3.5$  g/24 hours, measured by urine protein: creatinine ratio on a random urine sample.
19. Interstitial lung disease with ongoing signs and symptoms at the time of study registration.
20. Pleural effusion or ascites that causes respiratory compromise ( $\geq$  NCI CTCAE version 4.0 Grade 2 dyspnea).
21. History of organ allograft (including corneal transplant).
22. Known or suspected allergy or hypersensitivity to any of the study drugs, study drug classes, or excipients of the formulations given during the course of this trial.
23. Any malabsorption condition which, in the opinion of the treating physician, will affect the absorption of any of the agents used in this study.
24. Women who are pregnant or breast-feeding.
25. Any condition, which, in the site investigator's opinion, makes the subject unsuitable for trial participation.
26. Substance abuse, medical, psychological, or social conditions that may interfere with the subject's participation in the study or evaluation of the study results.
27. Treatment with any investigational agent within 28 days prior to registration.

### **3.3. Excluded therapies and medications, previous and concomitant**

1. Concurrent anti-cancer therapy (chemotherapy, radiation therapy, surgery, immunotherapy, biologic therapy, or tumor embolization) other than study treatment (regorafenib, other agents being investigated in combination with regorafenib)  
**NOTE:** Steroids for contrast related allergy or pain management are allowed.

2. Subjects on therapeutic anticoagulation will be excluded from study.

**NOTE:** prophylactic anticoagulation as described below is allowed:

- Low dose warfarin (1 mg orally, once daily) with PT-INR < 1.5 x ULN is permitted. Infrequent bleeding or elevations in PT-INR have been reported in some subjects taking warfarin while on regorafenib therapy. Therefore, subjects taking concomitant warfarin should be monitored regularly for changes in PT, PT-INR or clinical bleeding episodes.
- Low dose aspirin ( $\leq$  100 mg daily).
- Prophylactic doses of heparin. 40 mg daily

3. Subjects with prior history of a bleeding disorder will be excluded from study.

4. Concurrent use of any herbal remedy or preparation other than ginseng (e.g. St. John's wort [Hypericum perforatum])

#### **3.4. Inclusion of Women and Minorities**

Men and women of all races and ethnicities who meet the above-described eligibility criteria are eligible for participation in this study.

#### **4. SUBJECT REGISTRATION**

All subjects must be registered and randomized through the Hoosier Cancer Research Network (HCRN) electronic data capture (EDC) system.

Subjects must be registered and randomized prior to starting protocol therapy. Subjects must begin therapy **within 5 business days** of randomization.

#### **5. TREATMENT PLAN**

Regorafenib will be administered 160 mg once daily for the first 21 days of each 28-day cycle. Subjects that randomize to receive Ginseng will take 2,000 mg orally once daily every day for 8 weeks (2 cycles). Subjects that randomize to NOT receive Ginseng will not be given Ginseng. Subjects will be instructed to take regorafenib with a low-fat meal.

Subjects will undergo the fatigue assessments, using the MFSI-SF instrument and PROMIS according to the study calendar. Subjects will have a pill count C2D1 and at the end of treatment visit. Subjects will have the re-staging scan (CT of chest/abdomen/pelvis) at the end of Cycle 2/ week 8 ( $\pm 5$ ). See Study Procedures Manual for questionnaire administration and pill count instructions.

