## 7 STUDY SCHEDULE OF EVENTS

Cycle = 28 days

Examination	Screening		Cycle 1		Cycle 2		After completion of Cycle 2	End of Treatment Visit 	Follow up 
	-28 days	-7 days	Day 1	Day 15 (±3)	Day 1 (±3)	Day 15 (±3)	(±5)	30 days (± 7) after last dose of Cycle 2	(±7)
REQUIRED ASSESSMENTS									
Informed Consent	X								
Medical history	X								
Height	X								
Physical examination	X		X	X	X	X		X	
Vital signs including BP, weight and ECOG performance status	X	X 	X	X	X	X		X	
CBC w/ differential		X		X	X	X		X	
Complete Metabolic Profile 		X		X	X	X		X	
PT/INR and aPTT 		X	[D5]		[X]			X	
Pregnancy test 		X							
Urinalysis 		X	X		X				
AEs & concomitant medications	X		X	X	X	X		X	
DISEASE ASSESSMENT									
Pathology Review	X								
CT chest/abdomen/pelvis 	X						X 		
TREATMENT									
Regorafenib 			X	X	X	X			
Ginseng 			X	X	X	X			
OTHER									
MFSI-SF, PROMIS 			X		X 			X	
Pill count 					X			X	
FOLLOW-UP									
For progression, start of additional cancer treatment, and survival									X

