### 7.2.2 Cycle 1 Day 15 ( $\pm$ 3 days)

- Complete physical examination
- Vital signs including BP, weight and ECOG performance status
- Laboratory testing:
  - Complete Blood Count (CBC) with differential and platelet count
  - Complete metabolic profile (CMP)
- Adverse event and concomitant medication assessment
- Drug administration as outlined in Section 5 and Study Calendar
- Administer MFSI-SF and PROMIS questionnaires

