### **7.2.5 After completion of Cycle 2/ 8 weeks ( $\pm 5$ days)**

- CT scans of the chest, abdomen, and pelvis to assess all measurable or non-measurable sites of disease. Regardless of randomization, all subjects will follow up with their physician to discuss results.

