### **Analyses:**

The primary objective is to assess the effect of Ginseng on fatigue using the multidimensional Fatigue Symptom Inventory–Short Form (MFSI-SF) and PROMIS Short Form v1.0 – Fatigue 8a. Subjects will have fatigue assessed at baseline and at weeks 2, 4, and 8. Repeated measures analysis of covariance will be used to assess the effect of Ginseng on fatigue. An unstructured covariance matrix will be used initially to account for the within subject correlation in fatigue over time. Additional covariance structures (exchangeable, autoregressive, Toeplitz, etc.) will be considered to reduce the number of fitted parameters, and the final structure will be chosen based on likelihood ratio tests for nested structures and the AIC statistic for non-nested structures. The primary hypothesis will be assessed using a linear contrast at the end of cycle 1. Additional contrasts will be used to assess the difference in fatigue at each time as well as the average difference in fatigue over time.

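### The study calendar omits the two Day 15 fatigue questionnaires that Sections 7.2.2 and 7.2.4 require, and Section 11 analyses week 2 but not week 6

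*Combined protocol and SAP*

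**What the plan says.** Fatigue is the primary objective, measured by MFSI-SF and PROMIS. Three parts of the combined protocol and SAP say when it is measured.

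- **Calendar.** Section 5 sends the reader there: "Subjects will undergo the fatigue assessments, using the MFSI-SF instrument and PROMIS according to the study calendar". In the Section 7 schedule, the row "MFSI-SF, PROMIS" is marked at Cycle 1 Day 1, Cycle 2 Day 1 and End of Treatment. Both Day 15 columns are blank.
- **Visit lists.** Section 7.2.2 (Cycle 1 Day 15) says "Administer MFSI-SF and PROMIS questionnaires", and Section 7.2.4 (Cycle 2 Day 15) carries the same instruction. Cycle 1 Day 1, Cycle 2 Day 1 and End of Treatment also include the questionnaires.
- **Analysis.** Section 11, Analyses: "Subjects will have fatigue assessed at baseline and at weeks 2, 4, and 8". On the primary test it says: "The primary hypothesis will be assessed using a linear contrast at the end of cycle 1". Further contrasts are planned at each time and for the average over time.

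**The concern.** Each of the three places gives a different set of fatigue assessments. Section 11 relies on a week-2 score that the calendar does not collect, and leaves out a week-6 score that the visit lists do collect.

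The two disputed visits carry particular information. Regorafenib is scheduled on days 1 to 21 of each cycle, so Day 15 with its 3-day window (days 12 to 18) falls within dosing. Cycle 1 Day 1 is baseline, Cycle 2 Day 1 follows the week off drug, and End of Treatment is about a month after the last dose. The Day 15 scores are therefore the only scheduled post-baseline fatigue scores taken during regorafenib dosing. Section 1 says that symptoms are most marked towards the end of dosing in each cycle.

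At stake are the week-2 contrast, part of the time-averaged contrast, and the week-6 information. A patient-reported score that was not taken cannot be recovered later.

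**Working it through.** **1. The schedules side by side.**

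| Time | Calendar (Section 7) | Visit lists (7.2.1 to 7.3) | Section 11 |
|---|---|---|---|
| Baseline, C1D1 | yes | yes | yes |
| Week 2, C1D15 | no | yes | yes |
| Week 4, C2D1 | yes | yes | yes |
| Week 6, C2D15 | no | yes | no |
| Week 8, after Cycle 2 | no | no | yes |
| End of Treatment | yes | yes | no |

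Of Section 11's three post-baseline times, the calendar schedules one (week 4) and the visit lists two (weeks 2 and 4). The week-2 contrast has 0 scheduled observations under the calendar and up to 90 under the visit lists.

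**2. Is the calendar row misread?** The pill-count row, read by the same columns, gives Cycle 2 Day 1 and End of Treatment. That is what Section 5 states for pill counts, so the columns are aligned.

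**3. The plan's own figures.** Inputs from Section 11: 60 and 30 subjects, SDs 27.0 and 26.1, difference 17, two-sided 0.05.

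- SE = √(27.0²/60 + 26.1²/30) = 5.904, with Satterthwaite df 59.9. Power from the noncentral t is 80.9%, against 80% stated.
- Half-width = 1.96 × 27 × √(1/60 + 1/30) = 1.96 × 6.037 = 11.833, as stated.

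Both describe a single between-group difference and do not depend on the Day 15 scores. The primary contrast is at Cycle 2 Day 1, which the calendar and the visit lists both schedule.

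**4. Illustration for the time-averaged contrast.** Assumptions not in the plan: SD 27 at every visit, exchangeable correlation ρ, baseline adjustment, no dropout, normal approximation, and the same true difference of 10 at every visit. The 10 is Section 11's likely ginseng change of 20 less the 10 assumed without ginseng. For the mean of k post-baseline scores:

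SE = 6.037 × √[(1 + (k − 1)ρ)/k − ρ²], power = Φ(10/SE − 1.96).

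To isolate the loss of week 2, compare weeks 2, 4 and 8 (k = 3) with weeks 4 and 8 (k = 2). At ρ = 0.5:

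- k = 3: factor 2/3 − 0.25 = 0.417, SE 3.90, half-width 7.64, power 73%.
- k = 2: factor 0.75 − 0.25 = 0.50, SE 4.27, half-width 8.37, power 65%.

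The same step takes power from 70% to 60% at ρ = 0.3 and from 85% to 79% at ρ = 0.7. Without baseline adjustment (dropping the ρ² term), the half-width goes from 9.66 to 10.25 at ρ = 0.5.

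**The case against.** **Nothing in the documents ranks the calendar above the visit lists.** Sections 7.2.2 and 7.2.4 are direct instructions, and Section 11 expects a week-2 score. Section 5 and calendar footnote 6 also refer sites to a Study Procedures Manual that is not in these documents. This stands: the week-2 loss is conditional on a site working from the calendar. Section 5's sentence makes that likely enough to matter, but does not make it certain.

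**A reader might infer that the primary analysis is damaged, or that the averaged contrast has no data.** The documents support neither. The primary contrast is scheduled in both places, and the averaged contrast keeps week 4 even under the calendar.

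**A reader might also compare week 4 alone with weeks 2, 4 and 6.** By the formula above at ρ = 0.5, that gives 48% against 73% power. The arithmetic is right, but the one-visit case arises only because week 8 is also unscheduled, which is a separate gap. The Day 15 omission should not be charged with that difference.

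**The power comparison assumes a constant effect.** Averages over different visits are different estimands. If the week-2 difference were 5 (an assumption), the weeks 2, 4 and 8 average would be (5 + 10 + 10)/3 = 8.33 with SE 3.90, giving about 57% power. That is below the 65% for weeks 4 and 8. The gain in precision remains, but the gain in power depends on an early effect. The plan sets no power target for this contrast and does not expect significance.

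**Early dropouts are not necessarily without data.** Footnote 7 gives subjects who stop early an End of Treatment visit 30 days later, and Section 7.3 includes the questionnaires there. It would be too strong to say that a subject lost after week 2 contributes nothing. Section 11 does not say how that score is used.

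**Conclusion.** The three schedules conflict, and the conflict should be corrected. At any site that follows the calendar, the week-2 contrast has no data and the time-averaged contrast loses one time point. If sites follow different lists, week-2 data are missing by site. Where the visit lists are followed, the week-6 score, the only one scheduled during Cycle 2 dosing, is still outside the stated analysis.

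The size is moderate and confined to the additional contrasts. Under the assumptions shown, with ρ = 0.5, losing one of three time points costs about 0.7 units of half-width (7.64 to 8.37) and about 8 percentage points of power. Across ρ from 0.3 to 0.7 the power loss is about 6 to 10 points. The correlation and the constant effect are assumptions, so these figures are illustrations only.

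**What to change.** 1. In the Section 7 calendar, mark MFSI-SF and PROMIS at Cycle 1 Day 15 and Cycle 2 Day 15, to match Sections 7.2.2 and 7.2.4.
2. In Section 11, add week 6 to the list of fatigue assessments, so that it enters the repeated-measures model and the time-averaged contrast.
3. Do not delete week 8 from Section 11 as part of this change. It is the only planned score at the end of the 8-week ginseng course, yet neither the calendar nor the visit lists schedule it. Section 7.2.5 lists only "CT scans of the chest, abdomen, and pelvis to assess all measurable or non-measurable sites of disease", and the next questionnaire is at "30 days (± 7) after last dose of Cycle 2". Reconcile week 8 and the role of the End of Treatment score across the three places separately.

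Items 1 and 2 cost two calendar marks and one revised sentence, carried through the amendment approvals in Section 13.4. Subjects already attend both Day 15 visits. The downside is a few minutes of their time at sites now working from the calendar.

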## 5.1. Study Drug Administration

**Table 1: Study Drug Administration; One cycle is 28 days.**

Drug	Dose	Frequency of administration	Route of administration	Number of cycles
Regorafenib	160 mg	Days 1-21 of each 28-day cycle	Orally	2
Ginseng	1,000 mg	Twice a day (total of 2,000 mg per day) for 4 weeks (28 days)	Orally	2

### 5.1.1 Treatment Schedules

#### 5.1.1.1 Regorafenib

Regorafenib 160 mg PO once daily will be taken for 3 weeks on/1 week off for 2 cycles. Four 40-mg regorafenib tablets should be taken once a day with approximately 8 fluid ounces (240 mL) of water after a low-fat (<30% fat) meal. Some examples of a low-fat meal are:

- Two slices of white toast with 1 tablespoon of low-fat margarine and 1 tablespoon of jelly and 8 ounces (240 mL) of skim milk (approximately 319 calories and 8.2 g of fat).
- One cup of cereal (i.e. Special K), 8 ounces (240 mL) of skim milk, one piece of toast with jam (no butter or marmalade), apple juice, and one cup of coffee or tea (2 g fat, 17 g protein, 93 g of carbohydrate, 520 calories).

#### 5.1.1.2 Ginseng

Ginseng 2,000 mg per day will be taken for 4 weeks on for 2 cycles. **Dosing will be 1,000 mg PO twice a day.** The (4) 500 mg capsules consist of pure ground root of Wisconsin ginseng and should be swallowed whole. Do not chew, crush or break. May be taken with or without food. For subjects that randomize to ginseng, if regorafenib is held due to toxicity the ginseng may continue per protocol schedule.

### 5.1.2 Missed Doses

Missed doses can be within 4 hours of the time that the dose was scheduled. If the timing is beyond 4 hours, the subject will skip the dose and take the next dose as scheduled. Under no circumstances should a subject take two doses on the same day to make up for a missed dose from the previous day.

### 5.1.3 Pre-medications

Premedication is not required, but can be implemented per site investigator discretion.

### 5.1.4 Concurrent Therapy

All medication that is considered necessary for the subject's welfare, and which is not expected to interfere with the evaluation of the study treatment, may be given at the discretion of the site investigator. All medications (including contrast media) taken within 2 weeks prior to the start of the study and during the study must be recorded in the subject's source documentation and in the CRF (including start/stop dates, dose frequency, route of administration, and indication). Specific caution should be taken when considering or administering a concomitant medication

that is metabolized by the cytochrome enzymes CYP2C8, CYP2B6, and CYP2C9. Such concomitant medication should be avoided, if possible.

Co-administration of a strong CYP3A4 inducer (rifampin) with a single 160 mg dose of regorafenib decreased the mean exposure of regorafenib, increased the mean exposure of the active metabolite M-5, and resulted in no change in the mean exposure of the active metabolite M-2. Avoid concomitant use of regorafenib with strong CYP3A4 inducers (e.g. rifampin, phenytoin, carbamazepine, phenobarbital, and St. John's Wort)

Co-administration of a strong CYP3A4 inhibitor (ketoconazole) with a single 160mg dose of regorafenib increased the mean exposure of regorafenib and decreased the mean exposure of the active metabolites M-2 and M-5. Avoid concomitant use of regorafenib with strong inhibitors of CYP3A4 activity (e.g. clarithromycin, grapefruit juice, itraconazole, ketoconazole, nefazodone, posaconazole, telithromycin, and voriconazole).

Permitted concomitant therapy includes:

- Standard therapies for concurrent medical conditions.
- Supportive care for any underlying illness.
- Granulocyte colony-stimulating factor (G-CSF) and other hematopoietic growth factors may be used in the management of acute toxicity, such as febrile neutropenia, when clinically indicated or at the site investigator's discretion. However, they may not be substituted for a required dose reduction. Subjects are permitted to take chronic erythropoietin.
- Treatment with nonconventional therapies (such as acupuncture), and vitamin/mineral supplements are permitted if they do not interfere with the study endpoints, in the opinion of the site investigator.
- Bisphosphonates

The following are not permitted:

- Other investigational treatment during or within 30 days before starting study treatment
- Systemic antitumor therapy, including cytotoxic therapy, signal transduction inhibitors, immunotherapy, and hormonal therapy (other than testosterone supplements used to treat erectile dysfunction).
- Bone marrow transplant or stem cell rescue
- Subjects taking narrow therapeutic index medications should be monitored proactively (e.g. warfarin, phenytoin, quinidine, carbamazepine, Phenobarbital, cyclosporine, and digoxin). Warfarin is metabolized by the cytochrome enzyme CYP2C9 and its levels may be especially affected by regorafenib
- Use of any herbal remedy or preparation other than ginseng (e.g. St. John's wort [Hypericum perforatum])

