## 2. STUDY OBJECTIVES AND ENDPOINTS

### 2.1. Primary Objective

Assess the difference in fatigue scores using the Multidimensional Fatigue Symptom Inventory-Short Form (MFSI-SF) and Patient-Reported Outcomes Measurement Information System (PROMIS Short Form v1.0 – Fatigue 8a) for each group (Regorafenib+ No Ginseng vs. Regorafenib + Ginseng) to determine if 2000 mg of American Ginseng for 8 weeks has an impact on the fatigue score.

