### 6.3 Reasons for Withdrawal from Study

Subjects must be withdrawn from the trial (treatment and procedures) for the following reasons:

- Subject withdraws consent from study treatment and study procedures. A subject must be removed from the trial at his/her own request or at the request of his/her legally acceptable representative. At any time during the trial and without giving reasons, a subject may decline to participate further. The subject will not suffer any disadvantage as a result.
- Pregnancy. Pregnancy will be reported as an SAE. (Note: subjects who have been withdrawn from treatment with study drug because of pregnancy should not undergo CT scans [with contrast]/MRI or bone scans while pregnant.)
- If, in the site investigator's opinion, continuation of the trial would be harmful to the subject's well-being.
- Subject is lost to follow-up.
- Death.

Subjects **may be** withdrawn from the study for the following reasons:

- The subject is non-compliant with study drug, trial procedures, or both; including the use of anti-cancer therapy not prescribed by the study protocol.
- Severe allergic reaction to regorafenib (such as exfoliative erythroderma or Grade 3 or 4 hypersensitivity reaction) or ginseng.
- The development of a second cancer.
- Development of an intercurrent illness or situation which would, in the judgment of the site investigator, significantly affect assessments of clinical status and trial endpoints.
- Deterioration of ECOG performance status to 4.
- Use of illicit drugs or other substances that may, in the opinion of the site investigator, have a reasonable chance of contributing to toxicity or otherwise skewing trial result.

Any subject removed from the trial will remain under medical supervision until discharge or transfer is medically acceptable.

In all cases, the reason for withdrawal must be recorded in the eCRF and in the subject's medical records.

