## **9 DRUG INFORMATION**

The two drugs used in this trial are Regorafenib and Ginseng.

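### Both herbal-product rules exempt ginseng without limit by arm or source, so no visible on-study rule specifically bars control subjects from taking ginseng obtained elsewhere

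*Combined protocol and SAP*

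**What the plan says.** Two rules deal with herbal products, and both are written for all subjects.

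- Section 3.3, item 4, excludes "Concurrent use of any herbal remedy or preparation other than ginseng".
- Section 5.1.4, in its list of what is not permitted, has "Use of any herbal remedy or preparation other than ginseng".

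The one instruction for the control arm is in section 5: "Subjects that randomize to NOT receive Ginseng will not be given Ginseng". Section 9 explains why ginseng is exempted at all: "The two drugs used in this trial are Regorafenib and Ginseng".

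Other clauses bear on the matter without naming non-study ginseng:

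- Section 3.2, exclusion 1: "Subject should not be receiving any agent for fatigue including steroids or megace".
- Section 5.1.4 allows necessary medication that is "not expected to interfere with the evaluation of the study treatment, may be given at the discretion of the site investigator". It puts a similar non-interference condition on nonconventional therapies and supplements. It also requires all medications during the study to be recorded.
- Section 6.3 lists grounds on which a subject may be withdrawn. They include "The subject is non-compliant with study drug, trial procedures, or both" and the use of substances that the site investigator thinks could skew the result.
- Section 9.2, under treatment compliance, expects subjects to follow the whole protocol and lets the investigator discontinue those who do not.

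**The concern.** The trial compares ginseng with no ginseng (section 2.1), so the one herbal product that controls most need to avoid is the one both herbal rules leave out. A site that checks whether a control may take shop-bought ginseng will turn to those rules and find it exempt. The sentence in section 5 settles what the study supplies, not what a subject buys.

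Controls receive no capsules under the treatment plan. The synopsis does use the word placebo for the control group, but nothing in section 5 corresponds to it. Controls would therefore know that they are not assigned the remedy under test.

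A control who takes ginseng receives the test agent. If ginseng works, the difference between arms moves toward zero. Section 11 sorts the result by the observed difference (12 or larger, 8 to 12, close to zero) and uses the estimate and its interval to plan a follow-up trial, so dilution would feed into that decision.

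**Working it through.** **Reading the rules together.** The question is whether any visible clause is an on-study ban on non-study ginseng.

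- The two herbal rules exempt it by name.
- Section 5 concerns supply.
- Exclusion 1 is an entry criterion. It would keep out someone already taking ginseng for fatigue, but section 5.1.4 has no matching on-study ban.
- The non-interference conditions in section 5.1.4 depend on the investigator's judgement.
- The grounds in sections 6.3 and 9.2 are discretionary and act after the event.

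No clause is such a ban.

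**The plan's own figures (section 11).** Inputs: 60 and 30 subjects, SDs 27.0 and 26.1, two-sided 5% level, difference 17.

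- SE = √(27.0²/60 + 26.1²/30) = √(12.150 + 22.707) = 5.904.
- Satterthwaite degrees of freedom 59.9; power for 17 units 80.9%, against the stated 80%.
- Confidence interval half-width = 1.96 × 27 × √(1/60 + 1/30) = 11.833, as stated.

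**Illustration of dilution.** The documents give no rate of own use, so the following inputs are assumptions. Take a true difference D = 10, the middle of the 8 to 12 that section 11 expects. Let k of the 30 controls obtain a share e of the study effect. A late start or a lower dose means e below 1.

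- Mean difference = D × (1 − e × k/30).
- Chance of observing at least 8 = Φ((mean difference − 8)/5.904).

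| k of 30 | e | Mean difference | P(observed ≥ 8) | P(observed ≥ 12) |
|---|---|---|---|---|
| 0 | – | 10.0 | 63% | 37% |
| 1 | 1 | 9.7 | 61% | 35% |
| 3 | 1 | 9.0 | 57% | 31% |
| 6 | 1 | 8.0 | 50% | 25% |
| 1 | 0.5 | 9.8 | 62% | 36% |
| 3 | 0.5 | 9.5 | 60% | 34% |
| 6 | 0.5 | 9.0 | 57% | 31% |

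For k = 3, e = 1: 10 × (1 − 3/30) = 9.0, and Φ(1.0/5.904) = 0.567. Allowing for the extra spread from mixing users and non-users in the control arm raises the SE to at most 5.949 and moves these probabilities by about 0.002 at most.

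On the power scale at full effect, with 3 and then 6 of 30 controls using ginseng, power falls from 80.9% to 72.2% and 62.0% for a difference of 17, and from 38.5% to 32.3% and 26.6% for a difference of 10.

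One limit applies to the table. The primary contrast is at the end of cycle 1, while section 11 applies its bands to the difference at the end of the trial. The table uses one difference for both.

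**The case against.** The strongest reply is that this is ordinary drafting. Ginseng is a study drug, so a herbal ban without an exemption would prohibit the test treatment. Item 1 of section 3.3 makes a parallel exception for study treatment. The control arm is named for the absence of ginseng. Taking the test agent as a control is close to a textbook case of interfering with the evaluation, so the conditions in section 5.1.4 could be used to refuse it, and section 6.3 allows withdrawal for substances that skew the result. Non-study ginseng should also appear in the medication log.

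Much of this stands. The intent is clear, and an attentive investigator has the means to act on it. It does not close the gap, because the only rules specific to herbal products exempt ginseng by name, and the general clauses depend on judgement or follow the event. The bar on other investigational treatment does not clearly help either, since it most naturally means treatment other than the study drugs.

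It is also fair to say that the full-effect rows are an upper extreme. Section 9.1 chooses one Wisconsin product because ginseng is unregulated and varies as a crop, so a shop product may differ. A control would also have to start early to affect the end-of-cycle-1 contrast. Finally, an instruction against own use may be in the Study Procedures Manual or the consent form. If so, the exemption should still be brought into line with it.

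A reader might infer that the protocol means to let controls take ginseng, or that contamination will compromise the result. The documents support neither. The arm name and section 5 show the opposite intent, and no rate of use is given from which to predict any dilution.

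**Conclusion.** The point holds as a wording gap that is worth closing at low priority. Both herbal rules exempt ginseng for every subject, whatever its source, and the visible text contains no on-study ban on non-study ginseng for controls.

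The consequence depends on two things the documents do not settle: that some controls use ginseng, and that ginseng reduces fatigue. With no use nothing changes. On the assumed use shown the effect is modest: the mean difference stays at 8 or above in every case, and even 6 of 30 controls at full effect lower the chance of observing at least 8 from 63% to 50%. Section 11 itself does not expect the trial to reach significance, so what is at stake is mainly the estimate carried forward to the next trial.

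**What to change.** In section 3.3 item 4 and in the list of what is not permitted in section 5.1.4, replace *other than ginseng* with *other than study-supplied ginseng in subjects randomized to ginseng*. Apply it through the last fatigue questionnaire used in the analysis. Section 11 gives week 8 as the last assessment; the last questionnaire in section 7 is at the End of Treatment visit, about 30 days after treatment. The amendment should say which of the two ends the restriction.

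Record any non-study ginseng in the medication log that section 5.1.4 already requires, and report it by arm. Keep all randomised subjects in the primary contrast, whether or not they took it.

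No visits, forms or subjects are added. Subjects must forgo their own ginseng for the period. That includes ginseng-arm subjects after week 8 if the restriction runs to the End of Treatment visit. Under section 13.4 the change needs approval by each IRB and by the drug supplier, and by the local regulatory authority where applicable, so it is best bundled with another amendment.
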